#### **7.2.13 Clinical Pregnancy**

A transvaginal ultrasound of the uterus will be performed 5-6 weeks after transfer. Clinical pregnancy will be defined as at least one gestational sac, either intrauterine or ectopic. The inclusion of ectopic pregnancies and the lack of specification of heart beat in the definition of clinical pregnancy is in line with the current International Committee Monitoring Assisted Reproductive Technologies (ICMART) and World Health Organization (WHO) glossary on ART terminology.d,24 For intrauterine and ectopic pregnancies, the number of gestational sacs with fetal heart beat as well as without fetal heart beat will be recorded.

#### **7.2.14 Vital Pregnancy**

A transvaginal ultrasound of the uterus will be performed 5-6 weeks after transfer. Vital pregnancy will be defined as at least one intrauterine gestational sac with fetal heart beat 5-6 weeks after transfer.

d ICMART and WHO glossary on ART terminology: Clinical pregnancy – a pregnancy diagnosed by ultrasonographic visualization of one or more gestational sacs or definitive clinical signs of pregnancy. It includes ectopic pregnancy.

### **7.2.15 Ongoing Pregnancy**

A transvaginal or abdominal ultrasound of the uterus will be performed 10-11 weeks after transfer. Ongoing pregnancy will be defined as at least one intrauterine viable fetus. For ongoing pregnancies, the number of intrauterine viable fetuses will be recorded.

### **7.2.16 Ongoing Implantation**

Ongoing implantation is determined based on the ultrasound performed at the ongoing pregnancy visit. Ongoing implantation rate will be defined as the number of intrauterine viable fetuses 10-11 weeks after transfer divided by number of blastocysts transferred.

### **7.2.17 Early OHSS (including Moderate/Severe)**

Early OHSS is defined as OHSS with onset  $\leq$ 9 days after triggering of final follicular maturation. Classification of grade is according to a classification system based on Golan's classification system (see section 8.3.1 for details) and all OHSS cases will be graded as mild, moderate or severe.

### **7.2.18 Late OHSS (including Moderate/Severe)**

Late OHSS is defined as OHSS with onset  $>$ 9 days after triggering of final follicular maturation. Classification of grade is according to a classification system based on Golan's classification system (see section 8.3.1 for details) and all OHSS cases will be graded as mild, moderate or severe.

### **7.2.19 Adverse Events**

Adverse events will be recorded from the signed informed consent for participation in the trial until the end-of-trial visit. For each adverse event the following parameters are recorded by the investigator on the Adverse Event Log: description of event, date and time of onset, intensity, causal relation to IMP, action taken to IMP, other actions taken, seriousness of the adverse event, date and time of outcome, and outcome. Furthermore, the pattern (e.g. the frequency, time of onset, intensity, seriousness and outcome) of the most frequent / relevant adverse events will be tabulated.

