## 6.7 Oocyte Retrieval

Oocyte retrieval must take place 36h ( $\pm 2$ h) after hCG administration. All oocytes from follicles with an estimated diameter  $\geq 12$  mm should be retrieved. Below are listed the procedures related to the subjects attending the oocyte retrieval visit, while procedures related to the oocytes are described in section 6.8.

The following must take place at the oocyte retrieval visit:

- Blood collection for central laboratory analysis of endocrine parameters (treatment panel) preferably before oocyte retrieval procedure
- Oocyte retrieval
- Dispensing of progesterone for luteal support – must be started on the day after oocyte retrieval [*note*: only applicable for subjects who had oocytes retrieved]
- Drug accountability of hCG
- Recording of use of any concomitant medication
- Recording of adverse events

For subjects with oocytes retrieved, the next visit is the transfer visit 5 days after oocyte retrieval (section 6.9). Subjects having no oocytes retrieved will undergo end-of-trial assessments (section 6.13).

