## 6.13 End-of-trial

If a subject attends the scheduled trial visits, the end-of-trial assessments should take place at the last scheduled trial visit, i.e. for subjects with a confirmed vital pregnancy, the ongoing pregnancy visit would be the last scheduled trial visit and thus the visit where the end-of-trial assessments should be done.

The following procedures / assessments must take place at the last scheduled trial visit, irrespective of whether the subject discontinues the trial prematurely or completes it:

- Drug accountability, if applicable
- Recording of use of any concomitant medication
- Recording of adverse events
- Completion of end-of-trial form

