### **Adverse Events**

Adverse events will be coded using MedDRA. The version of MedDRA will be documented. Adverse events will be grouped according to start of FE 999049 as follows:

- Pre-treatment adverse event, i.e. any adverse event occurring after signed informed consent and before start of FE 999049 treatment, or a pre-existing medical condition that worsens in intensity after signed informed consent but before start of FE 999049 treatment.
- Treatment-emergent adverse event, i.e. any adverse event occurring after start of FE 999049 treatment and before the end-of-trial visit, or a pre-treatment adverse event or pre-existing medical condition that worsens in intensity after start of FE 999049 treatment and before the end-of-trial visit.

Treatment-emergent adverse events will be presented in summary tables and listings. Pre-treatment adverse events will be presented in a listing only. Treatment-emergent adverse events will be summarised overall and tabulated by System Organ Class (SOC) and PT in decreasing order of frequency. The total number of subjects reporting an adverse event, the percentage of subjects with an adverse event, and the number of events reported will be presented.

Summary tables will be produced for the following: all adverse events, adverse events by causality (reasonable possibility / no reasonable possibility), adverse events leading to death, adverse events by intensity (mild / moderate / severe), adverse reactions by intensity (mild / moderate / severe), serious adverse events, adverse events leading to discontinuation, adverse events with an incidence of  $\geq 5\%$  in any treatment group, and non-serious adverse events with an incidence of  $\geq 5\%$  in any treatment group.

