## 11.2 Adverse Events

Adverse events will be coded using MedDRA. The version of MedDRA will be documented. Adverse events will be grouped according to start of FE 999049 as follows:

- Pre-treatment adverse event, i.e. any adverse event occurring after signed informed consent and before start of FE 999049 treatment, or a pre-existing medical condition that worsens in intensity after signed informed consent but before start of FE 999049 treatment.
- Treatment-emergent adverse event, i.e. any adverse event occurring after start of FE 999049 treatment and before the end-of-trial visit, or a pre-treatment adverse event or pre-existing medical condition that worsens in intensity after start of FE 999049 treatment and before the end-of-trial visit.

Treatment-emergent adverse events will be presented in summary tables and listings. Pre-treatment adverse events will be presented in a listing only. Treatment-emergent adverse events will be summarised overall and tabulated by System Organ Class (SOC) and PT in decreasing order of frequency. The total number of subjects reporting an adverse event, the percentage of subjects with an adverse event, and the number of events reported will be presented.

Summary tables will be produced for the following: all adverse events, adverse events by causality (reasonable possibility / no reasonable possibility), adverse events leading to death, adverse events by intensity (mild / moderate / severe), adverse reactions by intensity (mild / moderate / severe), serious adverse events, adverse events leading to discontinuation, adverse events with an incidence of  $\geq 5\%$  in any treatment group, and non-serious adverse events with an incidence of  $\geq 5\%$  in any treatment group.

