### 14 Changes to the analyses described in the protocol

This SAP does not introduce any changes to the analyses already described in the trial protocol. A few additional details and clarifications have been added, and a few additional analyses have been added. These include the following:

- Addition of supplementary analyses based on subjects in the FAS starting treatment with FE 999049, i.e. analyses without the use of multiple imputations (this is the same as using the safety analysis set).
- Clarification that the analysis of number of MII oocytes will be based on subjects that had all their oocytes inseminated using ICSI, and subsequently multiple imputations will not be used.
- Addition of analyses for number of follicles, embryos, number of good-quality embryos, and number of blastocysts.
- Addition of analyses for number of stimulation days, total dose, and the average daily dose of FE 999049 treatment.

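### No analysis section lists the time-of-onset adverse event tabulation named in Protocol 7.2.19, and apart from early/late OHSS the planned tables pool follow-up windows whose length depends on pregnancy outcome

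*Protocol*

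**What the plan says.** Protocol 7.2.19 (Adverse Events) states that "the pattern (e.g. the frequency, time of onset, intensity, seriousness and outcome) of the most frequent / relevant adverse events will be tabulated". Onset date and time are recorded for every event (Protocol 7.2.19 and 8.2.2).

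The analysis sections do not take this up. The list in Protocol 9.6.3 begins "Summary tables will be produced for the following: all adverse events, adverse events by causality" and goes on to death, intensity, seriousness, discontinuation and incidence of at least 5%. SAP 11.2 repeats the list. Neither includes a table by time of onset. For the tables that are planned, the number of women with an event, "the percentage of subjects with an adverse event, and the number of events reported will be presented".

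The SAP defines a treatment-emergent event as "any adverse event occurring after start of FE 999049 treatment and before the end-of-trial visit", or as worsening of an earlier condition in that window. Under Protocol 6.13, "the end-of-trial assessments should take place at the last scheduled trial visit", and "for subjects with a confirmed vital pregnancy, the ongoing pregnancy visit would be the last scheduled trial visit". Women who leave earlier in the cycle have an earlier last visit (Protocol 6.6.4, 6.7, 6.10 and 6.11).

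OHSS is the exception. Protocol 9.6.3 and SAP 11.1 tabulate it as early or late, divided at 9 days after triggering.

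SAP 14 states: "This SAP does not introduce any changes to the analyses already described in the trial protocol".

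**The concern.** How long a woman contributes adverse events depends on how her cycle turns out. With an ongoing pregnancy she is observed about three times as long as after a negative test. Crude percentages and event counts over that window therefore depend partly on the pregnancy rate, which the trial also compares between arms.

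Comparing safety between the two arms is a secondary objective. SAP 11.2 lists counts and percentages without confidence intervals, so readers will compare the figures as printed. Some events can occur only in women who become pregnant: the pregnancy losses in Protocol 8.3.2 are adverse events of special interest. Others, such as nausea, fatigue and breast tenderness, are listed reactions to FE 999049 (Protocol 1.3) but could also arise in early pregnancy. A pooled table cannot show whether such an event began during stimulation or weeks after transfer.

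**Working it through.** **Inputs from the documents**

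- Trigger to retrieval: "Oocyte retrieval must take place 36h" (± 2 h) after hCG, taken as 1.5 days (Protocol 6.7).
- Retrieval to transfer: 5 days (Protocol 6.7).
- Transfer to last visit: 13-15 days after a negative test (6.10); 5-6 weeks, or 35-42 days, after a positive test without vital pregnancy (6.11); 10-11 weeks, or 70-77 days, with a vital pregnancy (6.12 and 6.13).
- Group size: 200 per arm (Protocol 9.1).
- Ongoing pregnancy rate: 30.7% with FE 999049 in ESTHER-1 (Protocol 1.1).

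The plan states no figure for adverse event windows or rates. Its one design figure, the ±1.4 half-width for oocytes, reproduces as 1.96 × 7.0 × √(2/200) = 1.37.

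**Assumptions**

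- Stimulation lasts 9-10 days. The documents give a maximum of 20 days but no mean. The ESTHER-1 mean total dose of 90 µg, at no more than 12 µg a day, implies a mean of at least 90/12 = 7.5 days.
- The daily risk of an event is constant and the same in both arms.
- 5% to 40% of women have an event within the short window.
- The comparison arm has 5 or 10 points more ongoing pregnancies than 30.7%.

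**Windows** = stimulation days + 1.5 + 5 + days from transfer to last visit

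| Outcome | 9 days | 10 days |
|---|---|---|
| Negative test | 28.5-30.5 | 29.5-31.5 |
| Positive test, no vital pregnancy | 50.5-57.5 | 51.5-58.5 |
| Ongoing pregnancy | 85.5-92.5 | 86.5-93.5 |

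With 9 days the midpoints for the first and last rows are 29.5 and 89 days, a ratio of 3.0. With 7.5 days of stimulation the ratio is 3.1; with 20 days it is 2.5. A cancelled cycle, or a retrieval with no oocytes, ends sooner than any row.

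**Mean follow-up per arm.** As a simplification, every woman without an ongoing pregnancy is given 29.5 days and the others 89 days. With ongoing pregnancy rate p, the mean is (1 − p) × 29.5 + p × 89.

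- p = 30.7%: 47.8 days
- p = 35.7%: 50.7 days (ratio 1.06)
- p = 40.7%: 53.7 days (ratio 1.12)

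**Percentage with an event.** Let r be the risk by 29.5 days. Under a constant hazard the risk by 89 days is R = 1 − (1 − r)^(89/29.5), and the arm's percentage is (1 − p)r + pR. The spurious difference between arms is therefore (p₁ − p₀)(R − r). For r = 20%, R = 49.0%, so 5 points gives 0.05 × 29.0 = 1.4 points and 10 points gives 2.9.

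| r | Percentage at p = 30.7% | 5 points more pregnancies | 10 points more pregnancies | 95% half-width, 200 per arm |
|---|---|---|---|---|
| 5% | 7.9 | +0.5 | +0.9 | 5.3-5.4 |
| 10% | 15.3 | +0.9 | +1.7 | 7.1-7.2 |
| 20% | 28.9 | +1.4 | +2.9 | 8.9-9.0 |
| 40% | 51.8 | +1.9 | +3.9 | 9.8 |

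The half-width is 1.96 × √(a₀(1 − a₀)/200 + a₁(1 − a₁)/200), where a₀ and a₁ are the two arms' percentages.

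For an event that occurs only in pregnancy, the difference is the gap in pregnancy rates times the event risk. For example, 10 points × 20% = 2 points.

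**The case against.** A reader might infer that the SAP dropped an analysis the protocol had planned. The documents do not support that. Protocol 9.6.3 already omits time of onset and the SAP carries that list over, so the mismatch begins inside the protocol, between 7.2.19 and 9.6.3. The SAP 14 statement of no change is accurate against protocol section 9. SAP section 2 also places the content and format of tables outside its scope, although it adds that these are described at about the protocol's level of detail.

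The commitment in 7.2.19 is also limited. Time of onset is one of several examples, only the most frequent or relevant events are covered, and no periods or denominators are set. Honouring it literally would leave the pooled window in every overall percentage. The missing tabulation and the pooling are related but separate points.

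The plan has partial safeguards. OHSS is split by onset, so it would be wrong to say that every adverse event percentage is pooled. Tables by causality, and of adverse reactions by intensity, should set aside some symptoms unrelated to FE 999049. Ordinary menstrual bleeding is not reported as an adverse event. All treatment-emergent events are listed.

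Finally, the arithmetic rests on hazards and pregnancy differences that the documents do not supply. Nothing in them anticipates different pregnancy rates in the two arms.

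All of this stands, and it limits the point. It does not remove it: a named tabulation has no table behind it, and the general percentages still cover windows of outcome-dependent length.

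**Conclusion.** The point holds as a cheap improvement to a descriptive safety analysis. The onset tabulation named in Protocol 7.2.19 appears in no analysis section, and the adverse event tables other than early/late OHSS pool windows of roughly 30 to 90 days according to outcome.

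Under a constant hazard, 5 points more ongoing pregnancies means about 6% more follow-up and 0.5-2 points more women with an event; 10 points means about 12% and 1-4 points. These figures depend on the assumed 9-10 stimulation days, the assumed 5-40% short-window risk and the two-group simplification. They shrink if events cluster around stimulation and retrieval. They are inside the 5-10 point half-width at 200 per arm.

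A reader might conclude that the arm with more pregnancies will look less safe. The documents support only that it can, if pregnancy rates differ; with equal rates the artefact is zero.

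**What to change.** In SAP 11.2 add a table of treatment-emergent events (all, serious, and the most frequent preferred terms) by period of onset:

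1. First FE 999049 dose to oocyte retrieval, or to end of stimulation if there is no retrieval, with all treated women as denominator.
2. From then to the βhCG visit, cut at day 13 after transfer because a negative test can end follow-up on that day.
3. Later.

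For periods 2 and 3, show the number at risk or exposure-adjusted rates. Add a note that the women still observed are selected by what happened after randomisation, so these comparisons are not protected by it. Period 1 does not depend on pregnancy. Its length still varies with stimulation days, which SAP 10.3 already compares.

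Keep the all-period table. Read the between-arm comparison alongside the period 1 table, without leaving later events out of the safety statement. List the addition in SAP 14, which also closes the gap between Protocol 7.2.19 and 9.6.3.

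The cost is SAP wording and a longer safety output. No new data are needed, since onset dates and times are already collected.

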### **7.2.20 Pen Malfunction**

Incidence of technical malfunctions of the pre-filled injection pen will be recorded.

## 7.3 Other Assessments

### 7.3.1 Demographics

Demographic information will be obtained during the screening period, including the following: date of birth, ethnicity (Hispanic or Latino, Not Hispanic or Latino) and race (American Indian or Alaska Native, Asian, Black or African American, Native Hawaiian or Other Pacific Islander, White). In countries where it is not allowed to collect 'date of birth' according to national regulations, 'age' will be collected at the screening and randomisation visits.

### 7.3.2 Medical History

Any relevant medical history will be recorded at screening. This includes diagnoses / symptoms and whether it is a past or ongoing occurrence.

### 7.3.3 Infertility History

Information about the reasons of infertility will be obtained during the screening period. Duration of infertility will be calculated at randomisation. This will also cover information about any previous treatment for infertility, including type of treatment and gonadotropin preparations used.

### 7.3.4 Menstrual History

Information about the menstrual history (average cycle length) will be obtained during the screening period.

### 7.3.5 Reproductive History

Information about the reproductive history will be obtained during the screening period. This will include number of clinical pregnancies, number of fetuses and outcome. Information on primary versus secondary infertility will be derived.

### 7.3.6 Smoking and Alcohol Habits

Information about smoking and alcohol habits will be obtained during the screening period. Smoking will be categorised as 0, 1-5 or 6-10 cigarettes per day. Alcohol will be categorised as 0, 1-7 or 8-14 units per week.

### 7.3.7 Body Measurements

Body measurements will be made at screening and stimulation day 1. Body weight will be measured without shoes and overcoat and using a calibrated scale. The body weight at stimulation day 1 will be used for dose calculation in the FE 999049 group. Height will only be measured at

screening and will be used to calculate BMI.

### **7.3.8 Physical Examination**

A complete physical examination will be performed at screening. Information will be recorded for general appearance, central and peripheral nervous system, head and neck (including ears, eyes, nose, mouth and throat), respiratory system, cardiovascular system, gastrointestinal system, lymphatic system, urinary system, musculoskeletal system and skin.

At screening, each category will be evaluated as normal, abnormal not clinically significant or abnormal clinically significant. Abnormal clinically significant findings at screening must be reported on the Medical History Log.

### **7.3.9 Gynaecological Examination**

A complete gynaecological examination will be performed at screening. Information will be recorded for breast, external genitalia, vagina, cervix, uterus, ovaries and fallopian tubes.

At screening, each category will be evaluated as normal, abnormal not clinically significant or abnormal clinically significant. Abnormal clinically significant findings at screening must be reported on the Medical History Log.

### **7.3.10 Endocrine Parameters at Screening**

At screening, the following panel of endocrine parameters will be evaluated: AMH, FSH, prolactin and TSH. The sample will be analysed at a central laboratory.

The results of the screening panel must be available prior to randomisation. The investigator will review and evaluate the laboratory results. The Laboratory Report will be signed and dated by the investigator.

### **7.3.11 Ovarian Volume**

As part of the transvaginal ultrasounds performed at stimulation day 1 and end-of-stimulation, the size – length, width and depth (recorded in mm) – of each ovary is measured and used for subsequent calculation of ovarian volume.

### **7.3.12 Endometrial Status**

Transvaginal ultrasound of the uterus to assess the endometrial status will be conducted at all visits during the stimulation period. The endometrial status assessments consist of the following

parameters: endometrial thickness, endometrial triple-layer structure and endometrial echogenicity pattern (*note*: the latter two are not assessed on stimulation day 1).

Endometrial thickness (composed of both layers of the endometrium) will be measured in the sagittal view of the uterus from the proximal and distal interfaces between the echogenic endometrium and the hypoechoic inner layer of the myometrium. Care should be taken not to include the hypoechoic subendometrial halo and to account for the presence of any fluid in the uterine cavity (not to be included in the endometrial thickness value). Endometrial thickness will be recorded in mm.

Endometrial triple-layer structure will be recorded as observed or not.

Endometrial echogenicity pattern will be recorded as hypoechoic, isoechoic, hyperechoic, or not possible to evaluate.

### **7.3.13 Blastocyst Transfer Procedure**

Any difficulty or eventuality during the transfer procedure will be noted.

### **7.3.14 Concomitant Medication**

The use of any concomitant medication within the last 3 months prior to informed consent for participation in the trial (except medication used in previous infertility treatment cycles) and throughout the trial will be recorded. Recording of concomitant medication will be performed at all visits. Any changes in concomitant medications or treatments must be recorded at each visit.

